7.5.2.2 Consistency of Treatment Effect in Subsets

The influence of baseline demographic and disease characteristics on the treatment effect among all randomized subjects will be explored via exploratory subset analyses. The median DFS based on KM product-limit method along with two-sided 95% CIs will be produced for the following subgroups.

A forest plot of the DFS hazard ratios (along with the 95% CIs) will be produced for each level of the subgroups examined. The analysis comparing treatment (i.e., Hazard Ratio) will be conducted if the number of subjects in the subgroup category is more than 10.

- Age category (< 65, ≥ 65 and < 75, ≥ 75; < 65 and ≥ 65)
- Gender (male, female)
- Race (White, Black or African American, Asian, Other)
- Region (Asia, RoW [including US/Canada, Europe])
- ECOG PS (0 vs. 1)
- Disease at study entry (EC, GEJ cancer)
 - EC: (Lower third, middle third, upper third)
 - GEJ cancer: Siewert-Stein (Type I vs. Type II vs. Type II)
- Disease stage at initial diagnosis (Stage I-II, Stage III-IV)
- Histology (stratification factor; squamous vs adenocarcinoma)
- Histological grade (G1/G2, G3/G4, GX)
- Pathologic lymph node status (stratification factor; ypN0 vs. ≥ ypN1)
- Pathologic tumor status (ypT0, ypT1/ypT2, ypT3/ypT4, unknown)

- Time from beginning of neoadjuvant CRT to complete resection (< 6 weeks vs. ≥ 6 weeks)
- Time from complete resection to randomization (< 10 weeks vs. ≥ 10 weeks).

- HER-2 status at study entry (negative, positive, unknown)
- Microsatellite instability (MSI-H, MSI-L, MSS, unknown)
- EBV status (positive, negative, unknown)
- Baseline PD-L1+ status based on a 1% cut off (≥ 1% vs. < 1% or indeterminate)
- Baseline PD-L1+ status based on a 5% cut off (≥ 5% vs. < 5% or indeterminate)
- Baseline PD-L1+ status based on a 10% cut off (≥ 10% vs. < 10% or indeterminate)

For the purposes of the subset analyses, stratification factors will be retrieved from the CRF.

7.5.2.3 Subjects follow-up for DFS

The currentness of follow-up for DFS is defined as the time between last tumor assessment date (regardless of initiation of subsequent therapy or second primary cancer) and cut-off date. Subjects who have a DFS event (regardless of initiation of subsequent therapy or second primary cancer)

and subjects with last tumor assessment date on or after data cut-off will be considered as current for this analysis.

The currentness of follow-up for DFS will be summarized by treatment group, and will be categorized in categories.

7.5.3 Secondary Efficacy Endpoints

7.5.3.1 Primary Analysis of OS

One of the secondary objectives of the study is to compare the overall survival between treatment groups in all randomized subjects.

Overall survival will be compared between the treatment groups at the two interim looks and final analyses, using the log-rank test, stratified by the three randomization stratification factors as recorded in IWRS. An O'Brien and Fleming α -spending function will be employed to determine the nominal significance levels for the interim and final analyses. The stratified hazard ratio between the treatment groups will be presented along with $100*(1-\alpha)\%$ CI (adjusted for interim). In addition, two-sided p-value will also be reported for the analysis of OS.

OS will be estimated using the KM techniques. A two-sided 95% CI for median OS in each treatment group will be computed via the log-log transformation method. OS rates at fixed time points (e.g. 6 months, depending on the minimum follow-up) will be presented along with their associated 95% CIs. These estimates will be derived from the Kaplan-Meier estimate and corresponding CIs will be derived based on Greenwood formula¹⁵ for variance derivation and on log-log transformation applied on the survivor function¹⁶.

The status of subjects who are censored in the OS KM analysis will be tabulated for each treatment group using the following categories:

- On-study (on-treatment, in follow-up)
- Off-study (lost to follow-up, withdraw consent, never treated)

A by-subject listing will be presented including treatment group, first and last dose date, whether the subject died, and if censored, the reason, event/censored date and OS duration.

7.5.3.2 Sensitivity Analyses

- The sensitivity analysis specified in [section 7.5.2.1](#) will also be performed for OS when applicable. The sensitivity analyses specific for DFS will not be performed for OS.

7.5.3.3 Consistency of Treatment Effect on OS in Subsets

The influence of baseline demographic and disease characteristics on the treatment effect among all randomized subjects will be explored via exploratory subset analyses. The median OS based on KM product-limit method along with two-sided 95% CIs will be produced for the subgroups listed in [Section 7.5.2.2](#) of this SAP.

A forest plot of the OS hazard ratios (along with the 95% CIs) will be produced for each level of the subgroups examined. The analysis comparing treatment (i.e., Hazard Ratio) will be conducted if the number of subjects in the subgroup category is more than 10.

For the purposes of the subset analyses, stratification factors will be retrieved from the CRF.

7.5.3.4 Subjects follow-up for OS

The extent of follow-up for survival, defined as the time between randomization date and last known alive date (for subjects who are alive) or death date (for subjects who died), will be summarized descriptively (median, min, max, etc.) in months for all randomized subjects.

The currentness of follow-up for survival, defined as the time between last OS contact (i.e., last known alive date or death date) and cutoff date (defined by last patient last visit date), will be summarized in months for all randomized subjects. Subjects who died and subjects with last known alive date on or after data cut-off date will have zero value for currentness of follow-up.

Minimum follow-up of OS for all randomized subjects, defined as the time from cutoff date to last subject's randomization date, will be summarized in months.

7.5.3.5 Survival Rate Analysis

Survival rate analysis will be carried out only for those time points which are mature enough by the time of the given database-lock - i.e. minimum follow-up must be approximately longer than timepoint to generate the rate.

Survival rates at 6, 12, 18, 24, 36, 48 months and at 5 years will be provided using KM product-limit method. (Note that survival rates at 1, 2, and 3 years are positioned as secondary endpoints.) For each survival rate per treatment arm, two-sided 95% CIs using will be computed using the Greenwood's formula for variance derivation and on log-log transformation applied on the survivor function $S(t)$.

Note that although not positioned as secondary endpoint, DFS rates will also be provided at the same timepoints as survival rates.

[REDACTED]

whereby the confidence interval will be adjusted accordingly (i.e. using the recalculated nominal α level at the final OS analysis).

If the trial is stopped for superiority of DFS and OS at the second interim, the p-value from the second interim stratified log-rank test will be considered the final primary analysis result.

7.6 Safety

7.6.1 Deaths

Deaths will be summarized by treatment group:

- All deaths, reasons for death.
- Deaths within 30 days of last dose received, reasons for death.
- Deaths within 100 days of last dose received, reasons for death.

A by-subject listing of deaths will be provided for the all enrolled subjects population.

7.6.2 Serious Adverse Events

Serious adverse events will be summarized by treatment group:

- Overall summary of SAEs by worst CTC grade (any grade, grade 3-4, grade 5) presented by SOC/PT.
- Overall summary of drug-related SAEs by worst CTC grade (any grade, grade 3-4, grade 5) presented by SOC/PT.

All analyses will be conducted using the 30-day safety window.

A by-subject SAE listing will be provided for the “enrolled subjects” population.

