3.5 Discontinuation of Subjects following any Treatment with Study Drug

Subjects MUST discontinue investigational product (and non-investigational product at the discretion of the investigator) for any of the following reasons:

- Subject's request to stop study treatment
- Recurrence (local, regional or distant)
- Any clinical adverse event (AE), laboratory abnormality or intercurrent illness which, in the opinion of the investigator, indicates that continued participation in the study is not in the best interest of the subject
- Termination of the study by Bristol-Myers Squibb (BMS)

- Loss of ability to freely provide consent through imprisonment or involuntarily incarceration for treatment of either a psychiatric or physical (eg, infectious disease) illness
- Unblinding a subject for any reason (emergency or non-emergency)
- Additional protocol specified reasons for discontinuation (see [Section 4.5.5](#))

This is a survival study; therefore subjects discontinuing study treatment will remain on study for documentation of progression and death.

In the case of pregnancy, the investigator must immediately notify the Sponsor or designee of this event. In most cases, the blinded study drug will be permanently discontinued. If the investigator determines a possible favorable benefit/risk ratio that warrants continuation of blinded study drug(s), a discussion between the investigator and the Sponsor or designee must occur.

All subjects who discontinue study drug should comply with protocol specified follow-up procedures as outlined in [Section 5](#). The only exception to this requirement is when a subject withdraws consent for all study procedures including post-treatment study follow-up or loses the ability to consent freely (ie, is imprisoned or involuntarily incarcerated for the treatment of either a psychiatric or physical illness).

If study drug is discontinued prior to the subject's completion of the study, the reason for the discontinuation must be documented in the subject's medical records and entered on the appropriate case report form (CRF) page.

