6 ADVERSE EVENTS

An *Adverse Event (AE)* is defined as any new untoward medical occurrence or worsening of a preexisting medical condition in a clinical investigation subject administered study drug and that does not necessarily have a causal relationship with this treatment. An AE can therefore be any unfavorable and unintended sign (such as an abnormal laboratory finding), symptom, or disease temporally associated with the use of study drug, whether or not considered related to the study drug.

The causal relationship to study drug is determined by a physician and should be used to assess all adverse events (AE). The causal relationship can be one of the following:

Related: There is a reasonable causal relationship between study drug administration and the AE.

Not related: There is not a reasonable causal relationship between study drug administration and the AE.

The term "reasonable causal relationship" means there is evidence to suggest a causal relationship.

Adverse events can be spontaneously reported or elicited during open-ended questioning, examination, or evaluation of a subject. (In order to prevent reporting bias, subjects should not be questioned regarding the specific occurrence of one or more AEs.)

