6.1 Serious Adverse Events

A **Serious Adverse Event (SAE)** is any untoward medical occurrence that at any dose:

- results in death
- is life-threatening (defined as an event in which the subject was at risk of death at the time of the event; it does not refer to an event which hypothetically might have caused death if it were more severe)
- requires inpatient hospitalization or causes prolongation of existing hospitalization (see **NOTE** below)
- results in persistent or significant disability/incapacity
- is a congenital anomaly/birth defect
- is an important medical event (defined as a medical event(s) that may not be immediately life-threatening or result in death or hospitalization but, based upon appropriate medical and scientific judgment, may jeopardize the subject or may require intervention [eg, medical, surgical] to prevent one of the other serious outcomes listed in the definition above.) Examples of such events include, but are not limited to, intensive treatment in an emergency room or at home for allergic bronchospasm; blood dyscrasias or convulsions that do not result in hospitalization.) Potential drug induced liver injury (DILI) is also considered an important medical event. (See [Section 6.6](#) for the definition of potential DILI.)

Suspected transmission of an infectious agent (eg, pathogenic or nonpathogenic) via the study drug is an SAE.

Although pregnancy, overdose, cancer, and potential drug induced liver injury (DILI) are not always serious by regulatory definition, these events must be handled as SAEs. (See [Section 6.1.1](#) for reporting pregnancies).

Any component of a study endpoint that is considered related to study therapy (eg, death is an endpoint, if death occurred due to anaphylaxis, anaphylaxis must be reported) should be reported as SAE (see [Section 6.1.1](#) for reporting details).

NOTE:

The following hospitalizations are not considered SAEs in BMS clinical studies:

- a visit to the emergency room or other hospital department < 24 hours, that does not result in admission (unless considered an important medical or life-threatening event)
- elective surgery, planned prior to signing consent
- admissions as per protocol for a planned medical/surgical procedure
- routine health assessment requiring admission for baseline/trending of health status (eg, routine colonoscopy)

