- medical/surgical admission other than to remedy ill health and planned prior to entry into the study. Appropriate documentation is required in these cases
- admission encountered for another life circumstance that carries no bearing on health status and requires no medical/surgical intervention (eg, lack of housing, economic inadequacy, caregiver respite, family circumstances, administrative reason).
- Admission for administration of anticancer therapy in the absence of any other SAEs

6.1.1 *Serious Adverse Event Collection and Reporting*

Sections 5.6.1-1 and 5.6.1-2 in the Investigator Brochure (IB) represent the Reference Safety Information to determine expectedness of serious adverse events for expedited reporting. Following the subject's written consent to participate in the study, all SAEs, whether related or not related to study drug, must be collected, including those thought to be associated with protocol-specified procedures. All SAEs must be collected that occur during the screening period and within 100 days of discontinuation of dosing. If applicable, SAEs must be collected that relate to any later protocol-specified procedure (eg, a follow-up skin biopsy).

The investigator must report any SAE that occurs after these time periods and that is believed to be related to study drug or protocol-specified procedure.

An SAE report must be completed for any event where doubt exists regarding its seriousness.

If the investigator believes that an SAE is not related to study drug, but is potentially related to the conditions of the study (such as withdrawal of previous therapy or a complication of a study procedure), the relationship must be specified in the narrative section of the SAE Report Form.

SAEs, whether related or not related to study drug, and pregnancies must be reported to Sponsor or designee within 24 hours of awareness of the event. SAEs must be recorded on the SAE Report Form; pregnancies on a Pregnancy Surveillance Form (electronic or paper forms). The preferred method for SAE data reporting collection is through the eCRF. The paper SAE/pregnancy surveillance forms are only intended as a back-up option when the eCRF system is not functioning. In this case, the paper forms are to be transmitted via email or confirmed facsimile (fax) transmission to:

SAE Email Address: Refer to Contact Information list.

SAE Facsimile Number: Refer to Contact Information list.

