7 STATISTICAL ANALYSES

7.1 General Methods

Unless otherwise noted, discrete variables will be tabulated by the frequency and proportion of subjects falling into each category, grouped by treatment. Percentages given in these tables will be rounded to the first decimal and, therefore, may not always sum to 100%. Percentages less than 0.1 will be indicated as ‘< 0.1’. Continuous variables will be summarized by treatment group using the mean, standard deviation, median, minimum, and maximum values.

Time-to-event variables (e.g. time-to resolution) will be analyzed using the Kaplan-Meier technique. When specified, the median will be reported along with 95% CI using Brookmeyer and Crowley method¹² (using log-log transformation for constructing the confidence intervals¹³).

The conventions to be used for imputing missing and partial dates for analyses requiring dates are described in [Section 8](#).

7.1.1 Adverse Events, Serious Adverse Events, Multiple events, Select Adverse Events, Other Events of Special Interest and Immune-Mediated Adverse Events

Drug-related AEs are those events with relationship to study drug “Related”, as recorded on the CRF. If the relationship to study drug is missing, the AE will be considered as drug-related.

Serious adverse events consist of AEs deemed serious by the Investigator and flagged accordingly in the CRF and clinical database.

Adverse events leading to study drug discontinuation are AEs with action taken regarding study drug(s) = “Drug was discontinued”.

Adverse events leading to dose delay are AEs with action taken regarding study drug(s) = “Drug was delayed”.

Adverse events leading to dose reduction are AEs with action taken regarding study drug(s) = “Dose was reduced”.

Adverse events will be coded using the Medical Dictionary for Regulatory Activities (MedDRA), and the most recent version of the dictionary at the time of the database lock will be used. Adverse event results will be graded for severity using the NCI Common Terminology Criteria for Adverse Events (CTCAE) and the version of the criteria specified in the protocol will be used.

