In the AE summary tables, unless otherwise specified, subjects will be counted only once at the Preferred Term (PT), only once at the System Organ Class (SOC), and only once at subject level for the counting of total number of subjects with an AE. The AE tables will be sorted by the SOC and then PTs. SOC will be ordered by descending frequency overall and then alphabetically. PTs will be ordered within SOC by descending frequency overall and then alphabetically. The sorting will be done based on the ‘Any Grade’ column of the experimental arm when arms are presented side-by-side.

Unless otherwise specified, the AE summary tables will be restricted to on-treatment events regardless of the causality.

Analyses that take into account the multiple occurrences of a given adverse event will be conducted (see [Section 7.6.9](#)). To prepare these analyses, the CRF data will be processed according to standard BMS algorithms¹⁴ in order to collapse adverse event records into unique records based on the preferred term. These data will be presented as the rate per 100 person-years of exposure. These analyses will take into account all on-treatment events (allowing more than 1 event per

subject) and the total exposure time. The person-year exposure will be computed as the sum over the subjects' exposure expressed in years where the exposure time is defined as

- (Date of last dose of study treatment - date of first dose of study treatment + 31 days (or 101 days, depending on the analysis))/365.25, for subject who are off study treatment and were followed for at least 30 days (or 100 days, depending on the analysis) after last dose of study treatment.
- (Last known alive date - date of first dose of study treatment +1)/365.25, for subjects who are still on-treatment or who are off study treatment and were followed less than 30 days (or 100 days depending on the analysis) after last dose of study treatment.

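### Protocol 6.1 leaves open whether recurrence of the study cancer is an SAE, and the SAP's any-cause safety totals include it wherever sites record it

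*SAP*

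**What the plan says.** **Protocol.** Section 6 defines an AE broadly, as "any new untoward medical occurrence or worsening of a preexisting medical condition". Section 6.1 states: "Although pregnancy, overdose, cancer, and potential drug induced liver injury (DILI) are not always serious by regulatory definition, these events must be handled as SAEs". Section 6.1.1 adds that "all SAEs, whether related or not related to study drug, must be collected". The same Section 6.1 also has a rule for endpoint events: "Any component of a study endpoint that is considered related to study therapy" is to be reported as an SAE. It does not say what to do with an endpoint event judged unrelated. Sections 6.1 and 6.1.1 list hospital admissions that do not count as SAEs, including admission to give anticancer therapy. Recurrence of the study cancer is not on that list, and no visible text exempts it. Section 3.5 makes recurrence a mandatory reason to stop study drug, as an item separate from clinical adverse events.

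**SAP.** The default in 7.1.1 is: "Unless otherwise specified, the AE summary tables will be restricted to on-treatment events regardless of the causality". Section 7.6.2 plans an "Overall summary of SAEs by worst CTC grade (any grade, grade 3-4, grade 5) presented by SOC/PT", and 7.6.3 and 7.6.5 plan matching any-cause tables for AEs leading to discontinuation and for all AEs. All use a window of 30 days after last dose, and none excludes recurrence or progression terms. Each section also has a drug-related version. An AE counts as leading to discontinuation if the action-taken field says the drug was discontinued (7.1.1).

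**The concern.** DFS is the primary endpoint, so the trial is designed on the expectation of fewer recurrences on nivolumab. If a recurrence is also entered as an AE or SAE, the same event counts once as efficacy and again in the safety totals, more often on placebo if the drug works. A true excess of SAEs on nivolumab would then look smaller in the all-cause total row. That row matters because a blinded all-cause comparison does not depend on the investigator's causality judgement. Its size also matters here because the subjects are disease-free at entry and benefit has to be weighed against added harm.

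The rows by SOC and preferred term would show recurrence terms separately. A reader still could not subtract them from the total, because a subject with recurrence may also have another SAE.

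**Working it through.** **Step 1: reproduce the plan's DFS figures.** The documents give no figure for the safety question itself, so the inputs come from SAP Table 5.1-1: control hazard 0.035 per month to month 12, hazard ratio 1 to month 3 and 0.667 afterwards.

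- Control, 12 months: exp(−0.035 × 12) = exp(−0.420) = 65.7%. The SAP states 65.7%.
- Nivolumab, 12 months: exp(−(0.035 × 3 + 0.035 × 0.667 × 9)) = exp(−0.315) = 73.0%. The SAP states 73.0%.

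**Step 2: share with a DFS event.** With 760 subjects at 2:1, the arms have about 253 and 507.

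| By month | Placebo | Nivolumab | Difference |
|---|---|---|---|
| 3 | 10.0% | 10.0% | 0 |
| 12 | 34.3% (about 87) | 27.0% (about 137) | 7.3 points |
| 13 | 36.2% | 28.5% | 7.8 points |

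Month 13 uses the next control hazard, 0.03.

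**Step 3: which month applies.** On schedule, Cycle 9 falls at Week 17 (day 113) and Cycle 17 comes 8 × 28 = 224 days later, on day 337. Adding 30 days gives day 367, and 367 / 30.4375 = 12.1 months. The month-12 figure is therefore the relevant one; month 13 needs dosing delays.

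**Step 4: carry this into a total row.** Let b1 and b0 be the risks of an SAE other than recurrence on nivolumab and placebo. Let r1 and r0 be the DFS-event shares from Step 2, and f the share of these recorded as SAEs. Treating recurrence as independent of other SAEs:

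observed risk = 1 − (1 − b)(1 − f·r)

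observed difference = (b1 − b0) − f × [r0(1 − b0) − r1(1 − b1)]

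The shift is exactly proportional to f. For b1 = 28% and b0 = 20%, the bracket at month 12 is 0.343 × 0.80 − 0.270 × 0.72 = 0.080. The values of b and f below are assumptions; the documents give none.

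| Assumed b1 vs b0 | True difference | f = 10% | f = 25% | f = 50% | f = 100% |
|---|---|---|---|---|---|
| 28% vs 20% | +8.0 | +7.2 | +6.0 | +4.0 | 0.0 |
| 30% vs 25% | +5.0 | +4.3 | +3.3 | +1.6 | −1.8 |
| 25% vs 15% | +10.0 | +9.1 | +7.8 | +5.6 | +1.1 |

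At full recording the shift is 6.8 to 8.9 points, around the raw 7.3-point gap. It departs from 7.3 because subjects who already have another SAE are not counted twice. At 10% recording it is 0.7 to 0.9 points.

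**Step 5: scale.** With SAE rates near 30% (assumed), the standard error of the arm difference is √(0.3 × 0.7 × (1/507 + 1/253)) = 3.5 points. The shift at half recording (3.4 to 4.4 points) is about one standard error.

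**The case against.** Several stronger readings are tempting, and the documents do not support them.

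- *Recurrence must be reported as an SAE.* This rests on one undefined word in Protocol 6.1. The endpoint sentence in the same section is more specific and can be read as leaving unrelated recurrences out. The text is unclear rather than explicit.
- *Every recurrence becomes an AE leading to discontinuation.* Protocol 3.5 lists recurrence apart from adverse events, and SAP 7.3.1 takes the reason for stopping from the subject status page. A recurrence enters the 7.6.3 table only if the site also records it as an AE with the drug-discontinued action.
- *No safety table removes it.* The drug-related tables omit recurrence judged unrelated, although a missing causality is counted as related (SAP 7.1.1). Protocol 6.2.1 requires tumor progression to be ruled out for immune-mediated AEs. Deaths are tabulated with reasons (SAP 7.6.1).
- *The toxicity of nivolumab is in fact offset.* That needs a real DFS benefit, which the design assumes to be absent in the first 3 months, and material recording of recurrence as an AE.

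Three further points stand. The month-12 gap counts all DFS events, including deaths without recurrence, and ignores subjects who stop early and leave the window 30 days after their last dose. Safety is an exploratory objective analysed descriptively, so no hypothesis test is affected. Some SAP safety text is redacted, and the CRF instructions and the sponsor's AE specification are not available; a rule on recurrence could sit there.

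None of this closes the gap in the visible text. The drug-related tables depend on attribution, which an all-cause comparison is meant to avoid.

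**Conclusion.** The point holds as an ambiguity in Protocol 6.1 with a conditional effect on the any-cause total rows of SAP 7.6.2, 7.6.3 and 7.6.5. If sites record recurrence and nivolumab reduces it, those totals understate the excess harm. The between-arm gap available to be recorded is at most about 7 points by month 12, and the effect falls in proportion to the recording share, to under 1 point at 10%. The exact shift in a total row also depends on overlap with other SAEs.

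The sizing assumes the SAP's DFS hazards, the DFS-event gap standing in for the recurrence gap, treatment to schedule, and independence of recurrence from other SAEs. The recording share is unknown, so the documents support neither a claim that the effect is large nor a claim that it is negligible.

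**What to change.** **SAP 7.6.2, 7.6.3 and 7.6.5:** keep the any-cause SAE, AE-leading-to-discontinuation and AE tables as they are. Beside each, add a supplementary version that excludes a pre-listed set of preferred terms for recurrence or progression of the esophageal or GEJ cancer. Report both totals in the arm comparison. The supplementary version should not replace the all-cause table, and deaths should not be removed by attributed cause, since that would bring back the causality judgement.

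**Protocol 6.1:** reconcile the statement on cancer with the statement on endpoint components, so that it is clear whether recurrence of the study cancer is recorded as an AE or SAE. This comes late. The current protocol is dated April 2024, treatment lasts at most 1 year, and the first interim, projected for about 12 months after last randomization, was complete by 2021. The sentence will mainly help interpretation; the tables can be run on data already collected.

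**Cost:** a term list, a few repeat tables, and two versions of the total row for readers to keep apart.
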